6. STATISTICAL METHODOLOGY FOR EFFICACY

The analyses of efficacy endpoints will be primarily based on the FAS. In addition, supportive analyses using the Per Protocol population and mITT might be conducted for the primary and the key secondary efficacy endpoints.

6.1. Analysis of Primary Efficacy Endpoint

The primary endpoint of the study is the change from baseline to Week 24 in the composite score of BME, synovitis, and tenosynovitis assessed by PsAMRIS.

Descriptive statistics of the baseline, post-baseline, change from baseline and percent change from baseline values will also be presented by the scanner type and the combination of both scanner types for the FAS.

The boxplots of change from baseline of primary efficacy endpoint over week 48 will be presented graphically.

Sensitivity analyses

The supportive/sensitivity analyses of the primary endpoint will be performed with the same analysis model based on PP population and mITT population.

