## 9.6. Efficacy Analysis

### 9.6.1. Primary Endpoint

The primary endpoint, change from baseline in the composite score of BME, synovitis, and tenosynovitis assessed by PsAMRIS at Week 24, will be analyzed descriptively. The 95% confidence interval will be provided for the mean change, and the composite score over time will be presented graphically.

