4.2.4.1. Magnetic Resonance Imaging (MRI)

In this study, the [REDACTED]

The MRI assessments will be conducted following the procedures outlined in the MRI manual, and must be performed on the same day of or within 7 days after the clinical visit. Therefore, the baseline MRI could be performed 7 days after the first administration of IP. The subsequent MRIs should be performed at Week 24 + 7 days and Week 48 + 7 days. All MRI visits should be scheduled well in advance to allow for proper planning. In addition, it is recommended to schedule 2 MRI visits (an initial and a repeat visit) for each MRI time point to ensure a high-quality MRI scan at each protocol-specified time point. The initial and repeat MRI visits should be scheduled approximately 7 to 14 days apart. If the initial MRI scans are of acceptable quality, then the scheduled repeat MRI session can be canceled. Maximum two repeated MRI scans can be scheduled. All images will be read regardless of deviations in acquisition window.

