4.2.4.4.2. Handling of Missing PsAMRIS Total Score Assessment

If a subject does not have any results within the visit window (referred to Section 4.2.4.1), the PsAMRIS results for this subject will be considered as missing at the time point, no imputation is needed and the detailed statistical analysis will be described in section 6.1

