5.2.2. Modified Intent to Treat (mITT)

The mITT will consist of all subjects who are in FAS, have baseline and at least one postbaseline of primary efficacy endpoint PsAMRIS. mITT might be the population for the sensitivity analysis for the primary efficacy endpoint if needed.

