5.5. Time Points

Time points in all analyses are based on the visits/study weeks as recorded in the database. Appropriate dates (e.g., date of measurement or date of specimen collection) will first be used to ensure only data (including data from scheduled, unscheduled and discontinuation) measured or collected within the specific analysis period (Section 5.3) are included, and then the visits/study weeks as recorded in the database will be used to assign one value (possibly missing) to each time point at the subject level according to the following rules:

Scheduled Visits

- If the value at a scheduled visit is missing but a value is available at an associated unscheduled visit, the value from the associated unscheduled visit will be used for the

study week. If values from more than one associated unscheduled visit (e.g., Visits 8.01 and 8.02) are available, then the one from the first associated unscheduled visit (e.g., Visit 8.01) will be used for the study week.

- If the value at a scheduled visit is missing and there is no value available from an associated unscheduled visit, the value at the study week will be missing.
- Please note that unscheduled visits are recorded to one general visit code. The visit numbering for unscheduled visits will be re-numbered based on the unscheduled visit date (and time) comparison to the schedule visit date (and time). If the unscheduled record falls in between two scheduled visits, the re-numbered value will be assigned. For example, if the unscheduled visit date is “on or after visit 1” AND “prior to visit 2”, then the re-numbered value will be 1.01. If there are multiple unscheduled visits in that interval, the unscheduled visit date (and time) will be used to ordered the re-number values like 1.01, 1.02, 1.03, so on.

Early Termination Visit

- A value from the early termination visit will be mapped to the next scheduled visit after the last visit the subject has completed.

Unscheduled Visit

- Please note that only vital signs, local lab data, central lab data and procedures MRI will have unscheduled visits and each unscheduled visit will be recorded to one specific visit code.

Analysis Visit Window for Safety Data

For safety analyses, all available values obtained between 2 planned visits including unscheduled measurements will be pooled to the analysis visit window according to the following definition:

Table 2: Analysis visit window for Safety Data

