6.2.2.1. Analyses of Continuous Secondary Endpoints Assessed by MRI

The analyses of secondary endpoints assessed by all MRI assessments will be performed in a manner similar as the primary analysis for primary endpoint (refer to Section 6.1) due to the impact from scanner type and baseline score and time.

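### Neither rerun that SAP 6.1 visibly names for the primary endpoint varies the assumption about subjects without a Week 24 score; for the observed mean change, the mITT rerun must reproduce the FAS result

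*SAP*

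**What the plan says.** Protocol 9.6.1 makes the primary analysis descriptive: "The 95% confidence interval will be provided for the mean change". SAP 5.2.1 takes the FAS (enrolled and dosed) as the primary efficacy population. SAP 5.2.2 defines the other set at issue: "The mITT will consist of all subjects who are in FAS, have baseline and at least one postbaseline of primary efficacy endpoint PsAMRIS". SAP 5.2.3 selects the PP population from dosed subjects by the absence of major violations that bear on the primary endpoint. It does not ask for a PsAMRIS score.

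A subject without a total score at a time point stays missing there. SAP 4.2.4.4.2 adds that "no imputation is needed and the detailed statistical analysis will be described in section 6.1". The readable part of 6.1 gives the endpoint, descriptive statistics by scanner type, boxplots, and then the sentence on reruns: "The supportive/sensitivity analyses of the primary endpoint will be performed with the same analysis model based on PP population and mITT population". The model is not visible. SAP 6.2.2.1 hints at its content, because it treats the MRI secondary endpoints in a similar way "due to the impact from scanner type and baseline score and time".

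Three provisions reduce the number of missing scores. For early termination (ET), SAP 5.5 says "A value from the early termination visit will be mapped to the next scheduled visit after the last visit the subject has completed". It also lets an unscheduled scan stand in: "If the value at a scheduled visit is missing but a value is available at an associated unscheduled visit", the unscheduled value is taken. SAP 4.2.4.1 says "All images will be read regardless of deviations in acquisition window". Against this, Protocol Table 13, footnote j, drops the ET scan when the previous scan is less than about 8 weeks old.

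**The concern.** The result is a mean change in one arm, so no control group can offset missingness that depends on response. SAP 8 lists lack of efficacy and adverse events among the reasons for stopping. If subjects who stop before Week 24 improve less, the mean among those scanned overstates the improvement in the FAS.

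Readers look to the sensitivity analyses to judge how far that could go. If FAS and mITT agree by construction, agreement reported under that label could be taken as reassurance that it cannot give. The stakes are limited: Protocol 1.3.2 seeks preliminary evidence and there is no formal test. What is affected is how far the Week 24 mean can be relied on.

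**Working it through.** **1. The plan's own figure.** SAP 4.3 gives SD 6.2, half-width 1.24, 120 subjects and about 20% dropout. Evaluable subjects: 120 × 0.80 = 96. Half-width: 1.96 × 6.2 / √96 = 1.240. The figure reproduces. The planning allowance is 24 of 120 subjects without data.

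**2. FAS against mITT for the observed mean change.** A Week 24 change needs a baseline score and a Week 24 score. An FAS subject with both has a baseline and a post-baseline score, so is in mITT by definition. An FAS subject outside mITT lacks one or the other and, with total scores not imputed, has no change value. Contributing subjects, mean, SD and interval are therefore identical. The ET and unscheduled-visit rules apply equally in both sets and do not alter this. In 2000 simulated data sets of 120 subjects with randomly missing scans, the contributing subjects were the same every time.

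**3. Under a model.** If change is modelled with baseline as a covariate, subjects with no change value add nothing to the fit, so the coefficients agree. Adjusted means can differ slightly if they are evaluated at the baseline average of the whole set. Results can also differ if baseline is modelled as an outcome. A second simulation of 2000 data sets used assumed inputs: gamma baseline with mean 16, slope -0.15 on baseline, residual SD 5.5, two scanners, FAS 120 and mITT 112. The FAS-mITT difference in adjusted means averaged 0.04 with a maximum of 0.23. In both sets the model is the same, so its missing-data assumption is the same.

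**4. PP.** This rerun can give another number, because violations remove subjects. It still uses observed scores only and assumes nothing different about unobserved ones.

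**5. Size, for an observed-case mean.** Let p be the fraction missing, m the mean change in those observed and d the mean change in those missing. The mean over all subjects is (1 - p)m + pd, so the shift is p(d - m). With d = 0 it is p|m|. The values of m are assumptions.

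For p, assume 8 subjects stop before Week 8, 6 in Weeks 8 to 16 and 6 in Weeks 16 to 24, and that every ET scan due is done. Footnote j removes the ET scan for the first 8.
- If the ET rule refers to any numbered visit, only stops after the Week 16 visit map to Week 24: (8 + 6)/120 = 11.7% missing.
- If it refers to the next MRI visit, all 12 later stops map to Week 24: 8/120 = 6.7% missing.

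| p | m = -2 | m = -3 | m = -5 |
|---|---|---|---|
| 6.7% | 0.13 | 0.20 | 0.33 |
| 11.7% | 0.23 | 0.35 | 0.58 |
| 20% | 0.40 | 0.60 | 1.00 |

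At m = -3 these are 16%, 28% and 48% of 1.24.

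**6. Size without assuming m.** A shift of a full half-width needs d - m = 1.24/p. That is 6.2 points (one planned SD) at 20% missing and 12.4 points at 10%.

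**The case against.** The strongest objection is that the planned rerun uses a model that the public copy does not show. Exact equality is proved for the protocol's observed mean, and no visible text says that this mean is the quantity rerun on mITT. SAP 4.2.4.4.2 also refers to 6.1 for the detailed analysis, and text not shown is not missing from the plan. This stands. A reader might infer that the SAP has no missing-data sensitivity analysis for the primary endpoint, or that mITT and FAS must agree exactly under the SAP's model. The documents support neither. A reader might also assume that PP is a subset of mITT. It is not, since PP requires no score.

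Second, the reruns are defined by population, and nothing visible claims that they test a missing-data assumption. A descriptive study may choose not to impute. This also stands in part: the point is an improvement, not an error in the plan.

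Third, the summaries report n (SAP 5.1) and the disposition tables report reasons for stopping (SAP 8), so readers will see that values are absent. That shows how many, but not where each Week 24 value came from or what the absent values could do to the mean.

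Fourth, the sizes depend on assumed inputs, and 20% is a planning allowance, not an expected count of missing Week 24 scores. This is accepted. At 10% missing, a full half-width shift needs a difference of two planned SDs.

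The ET mapping rule, and the conflict between firm wording in 6.1 and conditional wording in SAP 5.2.2 and Section 6, are separate wording matters. They do not support this point.

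**Conclusion.** The point holds within limits. The two reruns visible in SAP 6.1 leave the assumption about unobserved Week 24 scores untouched. For the observed mean change, the mITT rerun carries no information beyond the FAS result. For a model it would carry little or none.

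The effect on the estimate is unknown. In the illustration (mean change -3, no change in those missing) the shift is 0.20 to 0.35 at 6.7% to 11.7% missing and 0.60 at 20%, against 1.24. These figures rest on the assumed stops and means, and do not carry over to a model that uses other visits. They show that the question deserves an answer, not that the Week 24 mean is biased. Because the trial is descriptive and part of 6.1 is not visible, this is something to consider, held with medium confidence.

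**What to change.** Unless the unseen text of SAP 6.1 already contains one, add a sensitivity analysis over all FAS subjects with a baseline scan that varies the missing-data assumption. It can replace the mITT rerun or stand beside it. One example is delta-adjusted multiple imputation of the Week 24 change over a stated range of shifts, with the mean and 95% interval at each shift. The range should include zero change for subjects without a Week 24 value. Protocol 1.3.2 itself argues that MRI inflammation is not expected to improve much untreated, so zero is a natural point to include.

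Report how many subjects have a scheduled Week 24 scan, an ET or unscheduled scan assigned to Week 24, or neither.

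The cost is a change of SAP wording and one more program. The downside is that a less favourable sensitivity estimate may have to be reported.

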6.2. Analyses of Secondary Efficacy Endpoints

The secondary efficacy endpoints are divided into binary and continuous endpoints.

6.2.1. Analyses of Binary Secondary Endpoints

The binary secondary endpoints list is presented below:

- Proportion of subjects with baseline Leeds Enthesitis Index (LEI) whose LEI improves to 0 at Week 24 and Week 48

- Proportion of subjects with baseline SPARCC whose SPARCC improves to 0 at Week 24 and Week 48
- Proportion of subjects with baseline dactylitis whose tender dactylitis count improves to 0 at Week 24 and Week 48

For these binary endpoints, the number and percentages of subjects will be summarized by baseline and post-baseline visits, and the two-sided 95% Clopper-Pearson confidence intervals will be provided for the proportion. In addition, the proportion will be presented graphically. The number of subjects with missing values at each visit will be provided in a separate category.

6.2.2. Analyses of Continuous Secondary Endpoints

Due to the impact from MRI scanner type, the statistical method for the continuous secondary endpoints assessed by all MRI assessments (MRI of the most affected hand, WB-MRI, and DCE-MRI) will be different from other continuous secondary endpoints.

6.2.2.1. Analyses of Continuous Secondary Endpoints Assessed by MRI

The analyses of secondary endpoints assessed by all MRI assessments will be performed in a manner similar as the primary analysis for primary endpoint (refer to Section 6.1) due to the impact from scanner type and baseline score and time.

6.2.2.2. Analyses of Other Continuous Secondary Endpoints

Descriptive statistics (n, mean, SD, median, Q1, Q3, min, max) for observed values and changes from baseline (including percent changes from baseline, if needed) will be presented at specified time points among subjects who have both values at baseline and the time point of interest. In addition, two-sided 95% CIs based on normal distribution for mean changes (and percent changes from baseline) will be provided at each time point of interest. In addition, data will be reported based on the proportion of subjects above or below the smallest detectable changes (SDC).

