### 1.2.2.1.3. Efficacy Data From Phase 3 CC-10004-PSA-006 (ACTIVE) Through Week 24 in Subjects With an Inadequate Response to $\leq 1$ csDMARDs and Who Received Apremilast Monotherapy

The rapid onset of efficacy of apremilast monotherapy in biologic-naïve subjects who had received  $\leq 1$  csDMARDs was demonstrated in the ACTIVE study (CC-10004-PSA-006) (Nash, 2018), a Phase 3b multicenter, parallel-group study with 1 active treatment; overall treatment duration was 2 years. The study randomized 219 patients (APR 30 mg, n=110; placebo [PBO], n=109). At Week 16 (time of the primary endpoint), all subjects whose improvement was < 10% in both tender and swollen joint counts were eligible to enroll into an EE to active treatment with apremilast 30 mg BID. After 24 weeks of treatment, all subjects entered the active-treatment phase, in which they received apremilast 30 mg BID.

A separation in the proportion of ACR20 responders to APR versus PBO was noted at Week 2 (16.4% versus 6.4%; P=0.0252), the first Post-baseline Visit. Early onset of response to APR was observed across clinical assessments, with improvements in the Disease Activity Score (DAS)-28 C-reactive protein (CRP), SJC, HAQ-DI, enthesitis, and morning stiffness severity. Dactylitis and skin responses were not assessed in CC-10004-PSA-006.

A statistically significantly greater proportion of subjects in the APR 30 BID treatment group achieved the primary endpoint of ACR 20 response at Week 16 compared to placebo. A nominally significantly greater proportion of subjects in the APR 30 BID treatment group achieved an ACR 50 or ACR 70 response at Week 16 than in the placebo group (Table 5). Significant reduction in PsA disease activity/manifestations versus placebo was also demonstrated by changes in DAS-28 (CRP) (P<0.0001), SJC (P≤0.0001), and HAQ-DI (Table 6).

**Table 5: ACR 20/50/70 Responses at Weeks 16 and 24 During the Placebo-controlled Period in Study CC-10004-PSA-006 (FAS; NRI)**

Study CC-10004-PSA-006		
	Placebo N = 109	APR 30 BID N = 110
ACR 20		
Week 16 n (%)	22 (20.2)	42 (38.2)**
Week 24 n (%)	27 (24.8)	48 (43.6)**

**Table 5: ACR 20/50/70 Responses at Weeks 16 and 24 During the Placebo-controlled Period in Study CC-10004-PSA-006 (FAS; NRI) (Continued)**

Study CC-10004-PSA-006		
	Placebo N = 109	APR 30 BID N = 110
ACR 50		
Week 16 n (%)	5 (4.6)	20 (18.2)**
Week 24 n (%)	12 (11.0)	22 (20.0)
ACR 70		
Week 16 n (%)	0 (0.0)	7 (6.4)*
Week 24 n (%)	5 (4.6)	8 (7.3)

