**Table 6: HAQ-DI Score (0 to 3) Change From Baseline at Weeks 16 and 24 (FAS; MMRM)**

Visit Treatment Group	n a	Change From Baseline
		LS Mean (SE) b
Week 16		
Placebo	109	-0.055 (0.0513)
APR 30 BID	109	-0.205 (0.0523)*
Week 24		
Placebo	109	-0.169 (0.0581)
APR 30 BID	109	-0.273 (0.0572)

APR = apremilast; BID = twice daily; DMARD = disease-modifying antirheumatic drug; EE = early escape; FAS = Full Analysis Set; HAQ-DI = Health Assessment Questionnaire – Disability Index; LS = least-squares; MMRM = mixed-effects model of repeated measures; SE = standard error.

a Subjects with a baseline value and at least 1 postbaseline value (after exclusion of data for EE subjects) during the Placebo-controlled Phase are included in the MMRM analysis.

b The LS mean (SE) and 2-sided p-value are based on an MMRM analysis for the change from baseline, with treatment group, time, treatment-by-time interaction, and previous DMARD use and baseline oral glucocorticoids (prednisone or equivalent) use as factors and the baseline value as a covariate. An unstructured covariance matrix that is homogeneous across treatment groups was used. The p-values in italics are < 0.05 and are considered nominally significant, as hierarchical testing was stopped after the first secondary endpoint.

Among subjects with enthesitis at baseline, significant improvements from baseline in Gladman Enthesitis Index (GEI) score were observed with APR 30 mg (-1.1) versus placebo (-0.4) at Week 2 (P=.0354), as well as at Weeks 16 and 24 (Table 7).

In addition, numerically greater proportions of subjects treated with APR 30 mg (48.2%) compared to placebo (33.3%) achieved GEI scores of 0 at Week 24.

**Table 7: Gladman Enthesitis Index Change From Baseline at Weeks 16 and 24 During the Placebo-controlled Period in Subjects With Pre-existing Enthesopathy (FAS; MMRM)**

Treatment Group	n a	Change From Baseline	
		Week 16 LS Mean (SE) b	Week 24 LS Mean (SE) b
Placebo	48	-0.4 (0.26)	-0.5 (0.27)
APR 30 BID	49	-1.5 (0.26)**	-1.5 (0.26)**

APR = apremilast; BID = twice daily; DMARD = disease-modifying antirheumatic drug; EE = early escape; FAS = Full Analysis Set; GEI = Gladman Enthesitis Index; LS = least squares; MMRM = mixed-effects model for repeated measures; SE = standard error.

a Subjects with a baseline value and at least 1 postbaseline value at or prior to the respective visits are included.

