4.3. Sample Size and Power

While no MRI data are available for apremilast, assumptions used for the sample size calculation are primarily derived from the literature ([Glinatsi, 2015](#)). With an approximate 20% dropout rate, a sample size of 120 is required to produce a two-sided 95% confidence interval, for the expected change from baseline in the composite score of BME, synovitis, and tenosynovitis, with a distance from the mean to the limit equal to 1.24, assuming the standard deviation is 6.2.

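### Non-MRI continuous secondary endpoints are averaged only over subjects still observed, so improvement at Week 48 may be overstated for the FAS

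*SAP*

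**What the plan says.** SAP 5.2.1 and 6 make the FAS the main population for efficacy. For the continuous endpoints not read from MRI, SAP 6.2.2.2 gives descriptive statistics "among subjects who have both values at baseline and the time point of interest", with "two-sided 95% CIs based on normal distribution for mean changes".

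Several other rules decide who has a value:

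- **Missed visits.** Under SAP 5.5, if a scheduled visit has no value and no linked unscheduled value exists, "the value at the study week will be missing". The same section limits unscheduled visits to vital signs, laboratory data and MRI, so they do not help the clinical endpoints.
- **Early termination (ET).** SAP 5.5 assigns the ET value to the one scheduled visit that follows the last completed visit. It is not carried further.
- **Period.** SAP 5.3 uses only the treatment period for efficacy, and Protocol Table 13 schedules no efficacy assessment after ET.
- **Within-visit rules.** SAP 4.2.4.9 carries forward single joints that cannot be assessed, and the enthesitis indices refer to the same rule. HAQ-DI, BASDAI and PsAID-12 have item-level rules. None of these supplies a value for a subject who has left.
- **Supportive sets.** SAP 6 says that per-protocol and mITT analyses might be run for the primary and key secondary endpoints. Neither set recovers a missing Week 48 value.

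For the binary endpoints, SAP 6.2.1 says: "The number of subjects with missing values at each visit will be provided in a separate category". It does not say whether those subjects stay in the denominator. Protocol 9.1 left imputation rules to the SAP.

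**The concern.** Protocol 11.1 and SAP 8 both list lack of efficacy and adverse events as reasons for stopping. If subjects who stop have improved less, the mean among those who remain is too favourable as an estimate for the FAS. In a randomised trial, similar dropout in the control arm could offset part of this. Here nothing does, because the mean change is itself the result.

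The data needed to reduce the problem are already collected. Protocol Table 13 schedules joint counts, pain, both global assessments, HAQ-DI and the enthesitis and dactylitis measures at Weeks 8, 16, 24, 36 and 48. The SAP does not use the earlier visits to inform the later ones. The only reason SAP 6.2.2 gives for treating these endpoints differently from the MRI endpoints is scanner type, which has no bearing on dropout.

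**Working it through.** **Plan's own figure.** SAP 4.3 says: "With an approximate 20% dropout rate, a sample size of 120 is required to produce a two-sided 95% confidence interval", "with a distance from the mean to the limit equal to 1.24, assuming the standard deviation is 6.2". Check: (1.96 × 6.2 / 1.24)² = 9.8² = 96.04, and 96.04 / 0.80 = 120.05. The stated 120 reproduces. The planned half-width is 1.24 / 6.2 = 0.20 SD with about 96 subjects observed.

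**Inputs that the documents do not give.** Let m be the share of the FAS without a Week 48 value. Let d be the gap in mean improvement between subjects with and without a value, in SD units. The 20% dropout belongs to the primary-endpoint calculation, and using it for clinical endpoints at Week 48 is an assumption. The range for d is also an assumption.

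**Reference values for d.** Suppose leavers have no net change and stayers improve as the apremilast 30 mg groups did in HAQ-DI at Week 24 (Protocol Tables 2, 3 and 6). Then d is mean change / SD, with SD = SE × √n:

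| Study | Change | SE | n | SD | d |
|---|---|---|---|---|---|
| Palace 1 | 0.258 | 0.0371 | 168 | 0.481 | 0.537 |
| Palace 2 | 0.206 | 0.0372 | 162 | 0.473 | 0.435 |
| Palace 3 | 0.192 | 0.0353 | 167 | 0.456 | 0.421 |
| Palace 4 | 0.207 | 0.0369 | 176 | 0.490 | 0.423 |
| ACTIVE | 0.273 | 0.0572 | 109 | 0.597 | 0.457 |

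This gives d of about 0.42 to 0.54 SD. The SDs are back-calculated from least-squares standard errors, so they are approximate.

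**Bias and coverage.** The FAS mean is (1 − m) × observed mean + m × missing mean, so the observed-case mean exceeds it by m × d. In standard errors, b = m × d × √(120(1 − m)). Coverage of the FAS mean is Φ(1.96 − b) − Φ(−1.96 − b).

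Example with m = 0.20 and d = 0.25: b = 0.05 × √96 = 0.49, and coverage = Φ(1.47) − Φ(−2.45) = 92.2%.

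| Missing | d = 0 | 0.25 | 0.421 | 0.50 | 0.537 |
|---|---|---|---|---|---|
| 10% (n = 108) | 95.0% | 94.2% | 92.8% | 91.9% | 91.4% |
| 20% (n = 96) | 95.0% | 92.2% | 86.9% | 83.5% | 81.7% |

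A direct simulation at 20% and 0.50 SD gave 83.3%, against 83.5% from the formula. At 20% missing, coverage falls below 90% once d exceeds about 0.34 SD.

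**On the HAQ-DI scale.** At 20% missing with no net change in leavers, the overstatement is 0.20 × 0.192 = 0.038 (Palace 3) to 0.20 × 0.273 = 0.055 (ACTIVE) points.

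**What the ET rule does.** It lowers m at Week 48 only for subjects whose last completed visit was Week 36. For PsAID-12 and BASDAI, an ET value after a last completed visit at Week 24 goes to Week 36, where Table 13 does not schedule those instruments, so it informs neither reported time point.

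**The case against.** The strongest reply is that nothing here is certain. The documents give neither m nor d. A subject may stop for tolerability while responding, so even the direction is an assumption for adverse-event dropout. The ET rule brings in some leavers' last values. The interval keeps its nominal level for the subjects still observed, and the SAP states no estimand. These are secondary endpoints in an MRI study seeking preliminary evidence, Protocol 9.6.2 asks for descriptive analysis, and n at each visit will show how many are missing. All of this stands and limits the size of the point. It does not remove it, because the SAP names the FAS as its population and then averages a subset of it.

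A reader might infer several stronger things that the documents do not support:

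- **That the Week 48 intervals certainly fall well short of 95%.** This is conditional on m and d. Any estimate that ignores the ET rule describes a different plan.
- **That about 28% will be missing.** Protocol Table 10 shows 721 subjects in the first year and 520 in the second, so 27.9% did not continue. At that share, coverage for d of 0.421-0.537 would be 71-81%. But these are exposure-year counts from pooled earlier studies in csDMARD- and/or biologic-experienced subjects, not Week 48 missingness in this population.
- **That the programme's own practice settles the method.** ACTIVE used MMRM for HAQ-DI and non-responder imputation for response, in its placebo-controlled period. The long-term results in Protocol 1.2.2.1.4 to 1.2.2.1.6 are observed-case, and HAQ in the Palace studies used LOCF.
- **That the binary endpoints are also observed-case.** The denominator in SAP 6.2.1 is unstated. If the missing category stays in it, the percentage already equals non-responder imputation.
- **That normal rather than t quantiles matter.** With n = 96, the normal-quantile interval covers 94.7%.

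**Conclusion.** The point holds as a conditional one. SAP 6.2.2.2 is an observed-case analysis of the non-MRI continuous secondary endpoints, with no plan for subjects who leave. It overstates improvement for the FAS if leavers have done worse.

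At 20% missing, the bias is 0.05 SD for a 0.25 SD gap and 0.08-0.11 SD for a gap of 0.42-0.54 SD, against a half-width of 0.20 SD. Coverage of the FAS mean is then about 92% and 82-87% respectively. At 10% missing it is about 91-94% over the same gaps. It is 95% if dropout is unrelated to outcome. These figures assume an endpoint measured in all 120 subjects and equal SD in leavers and stayers. Endpoints limited to subjects with a manifestation at baseline have the same bias for the same m and d, but wider intervals and so less loss of coverage.

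For the binary endpoints the fault is an unstated denominator. The primary MRI endpoint is not affected. The change should be made, but the trial's main result does not depend on it.

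**What to change.** **SAP 6.2.2.2.**

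- Prespecify an MMRM on change from baseline, with visit and baseline value as terms and unstructured covariance, in all FAS subjects with a baseline and any post-baseline value. Keep the ET mapping.
- Report LS means with t-based 95% CIs at Weeks 24 and 48 next to the planned observed-case table, which still meets Protocol 9.6.2.
- For PsAID-12 and BASDAI, say how an ET value that maps to a visit without that instrument is used. A visit holding only leavers' values cannot support an unstructured covariance.
- Add one simple sensitivity analysis for leavers: either a delta adjustment or no net change from baseline.
- Say in one sentence which mean is the target, since the MMRM and the no-net-change analysis answer different questions.

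**SAP 6.2.1.** State that the denominator is all FAS subjects with the manifestation at baseline and that a missing value counts as non-response. Keep the separate count of missing values.

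**Cost.** SAP text and standard code, with no new visits or data. The MMRM assumes missing at random, which cannot be tested, and this is why the sensitivity analysis is needed. Reported improvements may be slightly less favourable.
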